2.6 Safety

The safety analyses will be based on the treated population. Adverse events and laboratories are graded and categorized using the CTCAE v5.0 criteria except where CTCAE grades are not available.

The following variables are summarized.

- Adverse events: worst CTCAE grade per patient (Table 12)
- Serious adverse events: worst CTCAE grade per patient (Table 13)
- Drug related adverse events: worst CTCAE grade per patient (Table 14)
- Drug related serious adverse events: worse CTCAE grade per patient (Table 15)

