5.0 PATIENT EVALUATION FLOWSHEET: PRE-TREATMENT, ON STUDY, AND AFTER TREATMENT

All patients entered on study must be evaluated according to the schedule outlined below with documentation submitted according to the schedule in Appendix III.

Required Investigations	Pre-study	During Protocol Therapy (start of treatment until the end of RT)	After Protocol Therapy until Recurrence/Progression	Post Recurrence or Local, Regional or Distant Progression ¹	
History and Physical Exam					
Including: height ² , weight, BSA, tobacco use, performance status, mucosal clinical assessment	≤ 28 days	Weekly	1, 3, 6, 9, 12, 15, 18, 21, 24, 28, 32, 36 months post RT then q6 months until 60 months post RT	q6 monthly from the date of first failure ³	
Direct or indirect visualization of tumour and surrounding area per local standards	≤ 8 weeks		3, 6, 9, 12, 15, 18, 21, 24, 28, 32, 36 months post RT then q6 months until 60 months post RT	At discretion of the investigator	
Laboratory Procedures/Assessments					
CBC with differential, creatinine, bilirubin, AST, ALT, ALP, LDH, albumin, total protein, glucose, magnesium, calcium, sodium, potassium, chloride, PTT, PT/INR			As clinically indicated		
TSH (Free T4 will be measured if TSH is abnormal)	≤ 14 days	As clinically indicated	12 and 24 months post RT	As clinically indicated	
Radiology					
CT or MRI of head and neck (MRI is recommended for base-of-tongue primary tumours)	≤ 8 weeks	Full staging required if failure documented during treatment	At 3 and 6 months post RT, and as clinically indicated	At the discretion of the investigator	
Chest CT or chest X-ray	As clinically indicated		As clinically indicated		
PET-CT scan	≤ 8 weeks		At the discretion of the investigator		
Adverse Events					
Adverse event assessment ⁴	≤ 14 days	Weekly	1, 3, 6, 9, 12, 15, 18, 21, 24, 28, 32, 36 months post RT then q6 months until 60 months post RT ⁵	As clinically indicated	
PRO-CTCAE selected items	≤ 14 days	Last week of RT	3, 6, 12, 24, and 36 months post RT		
Other Investigations					
Pregnancy Test ⁶	≤ 14 days				
Audiogram ¹¹	≤ 8 weeks		6 months post RT		
Tumour HPV status by IHC, PCR, or ISH ⁷	For all patients				
Biopsy ⁸		Recommended for confirmation of first recurrence, first distant metastases or first local/regional progression.			
Phone contact follow-up ⁹			Annually after 60 months post RT		

footnotes on next page ...

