
 As defined in Section 8. Height is only required at baseline. Weight and performance status only. Adverse events will be recorded and graded according to the CTCAE v 5.0 (Appendix VI). During the follow-up period, only treatment-related AEs will be collected. For women of child-bearing potential. May be urine or serum. Pregnancy test (in women of childbearing potential), as part of Pre-Study Evaluation, may include an ultrasound to rule-out pregnancy. HPV testing will be done locally. Reports showing positive immunostaining for p16 or positive HPV detection using PCR or in situ hybridization (ISH) must be submitted for each patient. Must be a needle core biopsy; FNA is not acceptable. Annual contact by phone or equivalent means to verify patient status, disease status and adverse events related to protocol treatment. The FACT-H&N questionnaire should be completed before the MDADI, EQ-5D-5L and PRO-CTCAE. Audiogram may be omitted at baseline and at the 6-month time point provided that this is aligned with institutional policy and there are no associated safety implications to the patient. If pre-registration audiogram is performed, it may be delayed until after enrollment but before commencement of therapy to accommodate delays in scheduling. The rationale for not ordering/delaying the test should be indicated in the source documentation 				

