1.1 Objective

To evaluate the efficacy of primary definitive radiotherapy (RT) or chemoradiotherapy (CRT) utilizing volume reduced elective nodal irradiation (ENI) as measured by 2-year event-free survival (EFS) in patients with low-risk HPV-related OPSCC.

Secondary objectives: To evaluate overall survival, local control, regional control, local-regional control, out-of-field regional control, distant metastasis free survival, early and late toxicities of treatment, subjective swallowing functions, quality of life (QOL), utilization of healthcare resources, work productivity, and prognostic biomarkers.

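### SAP 2.6 gives the AE tables no time period, so for events seen both early and late the late graded rate, part of a secondary objective, cannot be recovered

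*SAP*

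**What the plan says.** The objective is stated in protocol 1.2, protocol 13.1 and SAP 1.1 as "early and late toxicities of treatment". Neither document defines early or late or gives a cut point.

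SAP 2.6 plans four summaries. The line for all AEs reads "Adverse events: worst CTCAE grade per patient (Table 12". The other three apply the same highest-grade rule to SAEs in Table 13, to related AEs in Table 14 and to related SAEs in Table 15.

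The population is all treated patients (100 in SAP 1.6). In the table shells the columns are grades 1 to 5 and any grade, and the rows are categories and events. Tables 14 and 15 are split by attribution to radiotherapy or chemotherapy, not by time.

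On collection, the flowsheet in protocol 5.0 asks for AE assessment weekly during treatment and then at "1, 3, 6, 9, 12, 15, 18, 21, 24, 28, 32, 36 months post RT then q6 months until 60 months post RT". Its footnote adds: "During the follow-up period, only treatment-related AEs will be collected".

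**The concern.** A highest-grade-ever summary answers one question: how bad did this event get at any time? The objective asks two: how bad was it around treatment, and how bad was it later? If a patient has a severe acute event, the same event persisting or returning at an equal or lower grade leaves the table unchanged.

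The protocol background motivates smaller elective volumes by both the short-term and the long-term harm of standard treatment. In a single-arm trial the absolute late rate is the figure that a reader would set beside other series. The visits that would supply it are scheduled and dated, but the planned tables do not show it.

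A second problem concerns Tables 12 and 13. They are headed as all-cause, but the collection rule narrows once treatment ends, so one percentage rests on two definitions.

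**Working it through.** The plan states no figure for this point, so there is none to reproduce. The check sets the passages side by side and then shows what a pooled entry can and cannot reveal.

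**1. Is there a time split anywhere in the AE analysis?** SAP 2.6 names no window. The shells for Tables 12-15 have no period, visit or onset column. The SAP plans no time-to-onset, cumulative-incidence or by-visit analysis of AEs. It does use time elsewhere: assessment windows for QOL (2.8.2.1), change scores at each assessment (2.8.2.3), and a 30-day limit for on-trial deaths (2.7).

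**2. How much follow-up is pooled?** The final analysis is triggered at 304.7 person-years (SAP 1.2, 1.3). Dividing by the SAP 1.6 population sizes:

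- 304.7 / 99 = 3.08 years
- 304.7 / 100 = 3.05 years
- 304.7 / 103 = 2.96 years

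This is EFS follow-up, so it only approximates AE follow-up, but it extends well past the acute phase. On plan (3 years of accrual plus 2 of follow-up) individual follow-up runs from about 2 to 5 years from registration.

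**3. What does the pooled entry identify?** For one event at or above a given grade, let A be the proportion affected early, L the proportion affected late, and W the proportion in the pooled table. Then

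max(A, L) ≤ W ≤ min(1, A + L).

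From W alone, L can lie anywhere from 0 to W. If every late case is in a patient already affected early, as with persistence, then W = A and late cases add nothing.

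**4. Size, with assumed rates.** The documents give no toxicity rates. Taking early and late as independent, W = 1 − (1 − A)(1 − L):

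| Early A | L = 5% | L = 15% | L = 30% | Movement in W |
|---|---|---|---|---|
| 80% | 81% | 83% | 86% | 5 points |
| 60% | 62% | 66% | 72% | 10 points |
| 40% | 43% | 49% | 58% | 15 points |

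For a less common severe event, A = 30% and L = 5% give 1 − 0.70 × 0.95 = 33.5%, so the late cases add 3.5 points.

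The same entry also has several explanations. W = 62% arises from A = 62% and L = 0; from A = 60% and L = 5%; and from A = 40% and L = 36.7% (1 − 0.38/0.60 = 0.367).

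**5. Which tables mix collection rules?** The flowsheet's treatment column ends with RT. After that only treatment-related events are collected. Table 12 (all AEs) therefore joins two rules, as does Table 13 (all SAEs) if the footnote governs SAEs too. Protocol 9.0 asks for all SAEs to be recorded on case report forms without naming a period, so the rule for follow-up SAEs needs stating. Table 14 is limited to related events, which are collected in both phases, so it follows one rule. The same reasoning covers Table 15.

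**The case against.** The strongest reply is that the plan is less blind than it looks.

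- **Rows are by event.** A reader might infer that late toxicity cannot be read from the results at all. The shells do not support that. Protocol 2.0 names osteoradionecrosis, esophageal stricture and trismus; distinct terms of this kind have their own rows and are not hidden by an acute event of another name. The masking is confined to terms that occur in both phases. This stands.
- **Function is reported by visit.** FACT and MDADI are summarised to 36 months, with FOIS and PSS-HN by time period. This also stands, in part. These are mean changes in scales that serve separate listed objectives, and they are not graded toxicity rates. PRO-CTCAE is collected to 36 months, but the SAP sections and table shells contain no analysis of it.
- **Five years are not pooled.** A reader might take the 60-month schedule as the window. SAP 2.6 states no window, and follow-up averages about 3 years at the cut-off. On the planned 5-year timetable nobody reaches 60 months after RT, because RT itself ends some weeks after registration. Pooling to the cut-off is the natural reading of a table without a period, but it remains an inference.
- **It is descriptive, and the data are dated.** No test, decision rule or primary result changes, and period tables could be made later. True, but the cut point would then be chosen with the results in view.

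**Conclusion.** The point holds in limited form. A named secondary objective has two parts, and the planned AE tables do not separate them. For events common to both phases, the late graded rate is known only to lie between zero and the pooled entry. For late-only terms the tables remain informative, though on a denominator of all treated patients whether or not they were still being assessed.

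Two wider conclusions are not supported. The toxicity objective is not left wholly unanswered, given the event-level rows and the functional scales by visit. Late toxicity is also not the only rationale for the trial: the background cites acute harm as well.

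The mixed collection rule affects the all-cause tables (12, and 13 subject to the SAE rule noted above), not Table 14.

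The size figures rest on assumed rates and on independence of early and late events. They show how much information pooling loses and measure nothing observed in this trial. Neither the primary endpoint nor its analysis is affected.

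**What to change.** In SAP 2.6:

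1. State an early/late cut point. The 3-month post-RT visit is one option already in the schedule. Any cut is a convention and must be written down before tabulation.
2. Present the AE tables in two panels, with the worst grade per event taken within each period.
3. For the late panel, use as denominator the patients with at least one AE assessment in that period, and state that follow-up length varies. After recurrence the flowsheet asks for AE assessment only when clinically needed, so a note on this is also required.
4. Restrict the all-cause panels to the period when all AEs are collected. On the flowsheet that period ends with RT, which may be before the early/late cut, so the boundary should be stated separately. Say which rule applies to SAEs in follow-up.
5. Label the late panels as treatment-related only.

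The cost is extra table panels from data already dated by visit, plus a conventional cut point to defend. One limit remains: the worst grade in a late panel does not separate persistence from new onset. Grade by visit for a few key events common to both phases would show this if wanted.

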8.0 CRITERIA FOR MEASUREMENT OF STUDY ENDPOINTS

8.1 Definitions

8.1.1 *Evaluable for Adverse Events*

All patients will be evaluable for adverse event evaluation from the time of their first treatment.

8.1.2 *Evaluable for Quality of Life Assessment*

All patients who have completed the quality of life questionnaire are evaluable for quality of life.

8.1.3 *Evaluable for Health Economics Assessment*

All enrolled patients are evaluable for health economics. Those who have completed the resource utilization and lost productivity questionnaires will be evaluable for cost-utility analyses.

8.1.4 *Evaluable for Event-free Survival*

Event-free survival (EFS) is defined as the time from the date of registration to the date of first record of any of the following events:

- Investigator determined:
 - Local-regional progression or recurrence.
 - Distant metastasis.
- Surgery:
 - Surgery at any time for clinical or radiological (RECIST 1.1) disease persistence/progression/recurrence at the primary tumour site with tumour present/unknown on final pathology.
 - Neck dissection or surgery performed for clinical or radiological (RECIST 1.1) disease persistence/recurrence/progression within the target volumes > 20 weeks from the end of radiation therapy with tumour present/unknown on final pathology.
 - Neck dissection or surgery performed for clinical or radiological disease recurrence/progression outside the target volumes or without documentation of the site of failure at any time after registration with tumour present/unknown on final pathology.
- Non-protocol RT, chemotherapy, or biologic therapy (for the current cancer diagnosis) without documentation of the site of failure.
- Death due to any cause.

8.1.5 *Local-regional Control (LRC)*

Local-regional control is defined as the time from the date of registration to the date of any of the following, whichever comes first:

- Surgery of primary tumour at any time performed for clinical or radiological (RECIST 1.1) disease persistence/progression/recurrence with tumour present/unknown on final pathology

- Neck dissection > 20 weeks from the end of radiation therapy performed for clinical or radiological (RECIST 1.1) disease persistence/progression/recurrence within target volumes with tumour present/unknown on final pathology

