1.6 Data set descriptions

A total of 103 patients were enrolled in HN.10. Out of 103, 99 are eligible; 4 patients are ineligible. Three type of analysis samples will be used:

Population	Definition	Sample size	Analysis
All patients	All patients who have been enrolled.	103	Baseline characteristics
Treated patients	All patients who have received any protocol treatment.	100	Protocol therapy exposure, off treatment, Safety analysis
Eligible patients	All patients who satisfy all eligible criteria.	99	Efficacy, quality of life analysis

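### SAP Table 12 reports each patient's worst CTCAE grade without using the pre-study grade, so a symptom present before radiotherapy that persists unchanged on treatment can be counted as an adverse event

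*SAP*

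**What the plan says.** The flowsheet in Protocol 5.0 schedules adverse event assessment pre-study and then each week during therapy: "Adverse event assessment ⁴ ≤ 14 days Weekly". Grading is by CTCAE v5.0. A flowsheet footnote restricts collection to treatment-related events, but only for the follow-up period; no such limit is stated for the pre-study or on-treatment assessments. Protocol 8.1.1 adds: "All patients will be evaluable for adverse event evaluation from the time of their first treatment".

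SAP 2.6 sets the population ("The safety analyses will be based on the treated population", which SAP 1.6 puts at 100 patients) and then the summary rules: "Adverse events: worst CTCAE grade per patient (Table 12", "Serious adverse events: worst CTCAE grade per patient (Table 13", and "Drug related adverse events: worst CTCAE grade per patient (Table 14", with Table 15 for related serious events. It defines no start of the reporting window, no treatment-emergent event and no new-or-worsened rule. The Table 12 shell has columns for worst grade 1 to 5 and any grade, and none for baseline.

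**The concern.** A pre-study grade is collected and then used in no safety table. Consider a patient who enters with grade 2 throat pain from the tumour and stays at grade 2 throughout radiotherapy. If the symptom is logged at the weekly assessments, the worst-grade rule places that patient in the grade 2 column of Table 12, although nothing changed after treatment began.

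Early and late toxicity is a secondary objective, and lower toxicity is the rationale for reducing the elective volume. The trial has one arm, so no control group carries the same load of pre-existing symptoms, and a reader of Table 12 cannot separate that load from what treatment added. Any error overstates toxicity and so runs against the reduced-volume approach. The SAP does use baseline elsewhere: sections 2.8.2.3 and 2.8.3 analyse FACT-H&N, MDADI, FOIS and PSS-HN as change from baseline. It gives no reason for treating clinician-graded events differently.

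**Working it through.** The plan states no figure that this point would reproduce or change. The check has two parts.

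**1. Which tables can be affected**

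- *Purely pre-treatment records.* Protocol 8.1.1 starts evaluability at first treatment, so a record made only before treatment should fall outside the window. It does not say what happens to a baseline grade that is recorded again, unchanged, after treatment starts.
- *Table 12.* It has no attribution filter and no baseline comparison. An unchanged pre-existing symptom logged on treatment meets the stated rule.
- *Table 13.* Protocol 9.1 requires death, threat to life, hospitalization, disability or a similar outcome. A symptom grade that merely persists does not meet this.
- *Tables 14 and 15.* They ignore the baseline grade too, but they are limited to events attributed to radiotherapy or chemotherapy, which should remove most tumour symptoms.
- *Follow-up data.* Attribution is applied at collection, so late events are largely protected.

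What remains is Table 12 during treatment.

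**2. Possible size in one any-grade row of Table 12**

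Inputs:
- N = 100 treated patients (SAP 1.6).
- b = share with the symptom at baseline, persisting and recorded on treatment (assumed).
- p = share with a new or worsened event of that term, independent of b (assumed).

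Formulas:
- Counted under the stated rule: N[b + (1-b)p].
- Counted if new or worsened only: Np.
- Excess: N[b + (1-b)p - p] = Nb(1-p).

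Example: with b = 0.10 and p = 0.10, the stated rule counts 100 × (0.10 + 0.90 × 0.10) = 19, the new-or-worsened rule counts 10, and the excess is 9.

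| b | p | Stated rule | New or worsened | Excess |
|---|---|---|---|---|
| 10% | 10% | 19 | 10 | 9 |
| 10% | 30% | 37 | 30 | 7 |
| 10% | 60% | 64 | 60 | 4 |
| 10% | 90% | 91 | 90 | 1 |
| 30% | 10% | 37 | 10 | 27 |
| 30% | 30% | 51 | 30 | 21 |
| 30% | 60% | 72 | 60 | 12 |
| 30% | 90% | 93 | 90 | 3 |

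Independence is a convenience. In general the excess is N × b × (share of patients with a baseline symptom who do not worsen), so it lies between 0 and Nb. A patient whose baseline symptom worsens is counted under both rules, at the same worst grade.

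**The case against.** The SAP is silent rather than wrong. Whether an unchanged symptom is logged as an adverse event depends on the case report forms and on the data management plan cited in SAP 1.4, neither of which is available here. Showing the worst grade regardless of cause beside attribution tables is a legitimate descriptive choice. The attribution tables bear most directly on toxicity of treatment, and swallowing function is already analysed against baseline. No toxicity hypothesis, threshold or stopping rule rests on Table 12.

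Most of this stands, and it limits the point to what can happen under the stated rule. It does not remove the point. Table 12 is the only adverse event table, other than that for serious events, with no attribution filter. Attributing throat pain or dysphagia to tumour or treatment during oropharyngeal radiotherapy is a judgement, and a recorded baseline grade would inform it.

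A reader might infer more: that tumour symptoms are certainly counted, across all the safety tables, by the full number of patients who enter with them, and most of all for swallowing and pain. The documents do not support that. No text says unchanged symptoms are logged weekly. Serious, treatment-related and late events are protected as set out above. The full baseline share is only an upper bound, reached when none of those patients worsens. The excess shrinks as p rises, and Protocol 2.0 names swallowing and salivary impairment among the significant toxicities of this treatment, so those terms should be among the less distorted.

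**Conclusion.** The point holds in a limited form, as a desirable clarification. Under the rule as written, a pre-existing symptom that persists unchanged on treatment can be counted in Table 12. With assumed b of 10% to 30%, the excess in one any-grade row is 9 to 27 of 100 patients for a symptom that treatment seldom causes or worsens (p = 10%), and 1 to 3 for a near-universal acute toxicity (p = 90%). Both b and p are assumptions; the documents give neither. The result also assumes that unchanged symptoms are entered at the weekly assessments. The primary event-free survival analysis is not affected.

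**What to change.** In SAP 2.6, state that Table 12 covers events from first protocol treatment, consistent with Protocol 8.1.1. Then do one of the following:

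- count a CTCAE term only if it is new or of higher grade than at the pre-study assessment; or
- keep the worst on-treatment grade and show the pre-study grade beside it.

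Either needs one derived variable from an assessment the protocol already requires, and no new data. The first option has a small downside: a pre-existing symptom that would have resolved but persists because of treatment is no longer counted. The second avoids this, at the price of a wider table. Table 13 needs no change.

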2.7 Off treatment

- Number and (%) of patients and reasons off protocol treatment (Table 16).
- Deaths during protocol treatment or within 30 days of last protocol treatment: number of patients who died and cause of death from Date/Cause of Death Section of Death Report (Table 17)

2.8 Quality of life analysis

The quality of life of patients in this study is assessed at baseline, last week of RT, and 3, 6, 12, 24, 36 months post RT using FACT-G, FACT-H&N and MDADI.

2.8.1 Definitions and scoring

2.8.1.1 FACT-G

There are four functional domains from FACT-G questionnaires (see below for definitions). The scores are calculated by the corresponding formula below.

Physical well being: Questions: 1-7 (PWB)

Score=missing if number of above questions not answered is greater than 3; Otherwise,
Score = $(4 - (\text{Total for the answered questions} / \text{Total questions answered})) * 7$

Social/Family well being: Questions: 8-14 (SFWB)

Score=missing if number of above questions not answered is greater than 3; Otherwise,
Score = $(\text{Total for the answered questions} / \text{Total questions answered}) * 7$

Emotional well being: Questions: 15-20 (EWB)

Score=missing if number of above questions not answered is greater than 2; Otherwise,
Score = $(4 - (4 - \text{score of GE2} + \text{total of GE1, GE3-6}) / \text{Total questions answered}) * 6$ if GE2 is not missing with other missing treated as with value of 0; or
= $(4 - (\text{total score of GE1, GE3-6} / \text{Total questions answered}) * 6$ if GE2 is missing with other missing treated as with value of 0.

Functional well being: Questions: 21-27 (FWB)

Score=missing if number of above questions not answered is greater than 3; Otherwise,
Score = $(\text{Total for the answered questions} / \text{Total questions answered}) * 7$.

The FACT-G Total score = $(\text{PWB} + \text{SFWB} + \text{EWB} + \text{FWB})$ when the overall item response rate is greater than 80% (e.g. at least 22 of 27 FACT-G) items complete, otherwise, FACT-G total score is considered to be missing.

